Asking participants to withhold medication for Off-state examinations imposes a burden, but the Off-state (12 hours off meds) will increase insight into the direct effect of exercise on PD itself. Since medication changes are frequent with PD and often result in symptomatic fluctuations, the Off-state provides a more reliable, less confounded time comparisons. Medication reconciliation will be completed at each examination, and levodopa equivalent daily doses (LEDDs) will be determined and utilized in the prediction model (Aim 4). To determine the potential impact of overall physical activity in disease progression, all patients will be provided a Garmin activity monitor to measure overall daily activity (e.g., active minutes and steps per day). Currently, the Garmin activity monitor is utilized by 30,000+ participants in the CC Health System employee health plan, and accurately counts steps and activity levels of individuals with PD.³² Patients will wear the device on their belt/waistband or shoe during waking hours and upload the data every 30 days via the supplied application. Device batteries typically last ~6-months. To ensure no loss of data the battery will be replaced at the 6 month assessment. Activity monitor data will be synchronized with the secure CC Health system portal and downloaded to the [name] research server behind the CC firewall. The number of steps and minutes of activity, binned by day, week, month and year, will be considered for inclusion in the predictive model in Aim 4.

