Standardized High-Intensity Home Exercise Program: The Peloton platform contains thousands of pre-recorded cycling classes with varying levels of intensities and recommendations. Study staff will select cycling protocols from this pre-recorded list for cyclists entering the study at different levels of fitness (beginners, intermediate, or advanced). Participants will be safely increased in RPMs, heart rate, and overall levels of perceived exertion over subsequent weeks of the study to reach study recommendations. Participants will be will be asked to exercise on the Peloton 3 times per week for 50-60 minutes (40 minutes at their target HRR + 5-10 minute warm-up and cool-down) for 12 months and encouraged to exercise using a relatively high cadence (80-90 rpms). To increase engagement, modules containing different professional Peloton instructors will be utilized. All instances of the modules will be similar in terms of aerobic intensity; however they will vary in type of background music and general personality of the instructor. In addition to the selected CYCLE modules, the patient will have the option to join more than 20 daily "live" sessions or select one of 300+ scenic courses on the Peloton platform. These additional options empower each patient to exercise in a manner best suited for them and will facilitate compliance. Considering the Peloton records, stores, and transmits heart rate, power, speed, estimated distance, time and cadence for every exercise session, regardless of whether the patient is completing a CYCLE module, live class or scenic ride, the specific module they complete is not critical as data are recorded, transmitted and downloaded to the study database regardless. Secure data transmission procedures are detailed in Protection of Human Subjects.

Study staff at each site will make bi-monthly calls to patients to address technology issues or compliance obstacles for those patients not meeting exercise recommendations. During these calls, exercise may be

progressed as deemed appropriate based on physiological signs monitored by the Peloton and patient subjective report (see Protection of Human Subjects for details).

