- iii. Working memory/set switching: the ratio of time to complete the Trail Making Test B to time to complete the Trail Making Test A.

Descriptive/exploratory motor outcomes are:

- i. Cardiovascular fitness: Six Minute Walk Test distance;
- ii. Postural stability:
 - a. Balance Error Scoring System (BESS) double leg area
 - b. Balance Error Scoring System (BESS) tandem area
 - c. Balance Error Scoring System (BESS) double leg volume
 - d. Balance Error Scoring System (BESS) tandem volume
- iii. Total self-reported falls during the one-year observation period.

Descriptive/exploratory non-motor outcomes are:

- i. Movement Disorder Society Unified Parkinson's Disease Rating Scale Part I: Non-Motor Aspects of
- ii. Experiences of Daily Living (nM-EDL)
- iii. Movement Disorder Society Unified Parkinson's Disease Rating Scale Part II: Motor Aspects of Experiences of Daily Living (M-EDL)

iv. Movement Disorder Society Unified Parkinson's Disease Rating Scale Part IV: Motor Complications. The latter two scales are classified as non-motor rather than motor outcomes because they focus on patient-reported experience of functional and social impacts of the effects of motor symptoms rather than on the symptoms themselves.

Analysis Sets

The inferential and safety analysis set will consist of all randomized patients. The descriptive/exploratory analysis set will consist of all randomized patients who complete baseline procedures for initiating randomized treatment and follow-up, and for whom study follow-up is initiated. Descriptions of baseline variables will use all available data in the inferential and safety analysis set. Inferential and safety outcomes will be analyzed using the inferential and safety analysis set in accordance with the strict intention-to-treat principle, under which all randomized patients are included in analyses in accordance with their randomized treatment assignments, regardless of their post-randomization experience including treatment and dropout from treatment or study. Descriptive/exploratory outcomes will be analyzed using the descriptive/exploratory analysis set.

Missing Data

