In inferential analyses we will presume that missing observations, for whatever reason they may be missing, are technically “missing at random,” i.e., that the unobserved data come from the same distributions, conditional on other variables that have been ascertained in CYCLE II, as do the observed data. Under this assumption, we will multiply impute missing data using both baseline variables and outcome data and will include the multiply imputed outcome data in analyses. Specifically, missing data will be multiply imputed by sequential chained equations using fully conditional specification and the following sets of predictors:

- i. baseline sociodemographic and other characteristics: age, sex, race, ethnicity, residential living situation (alone, with family member or friend, with significant other), employment status (full-time, part-time, retired due to Parkinson's disease related disability, otherwise retired), body mass index (BMI), hand dominance;
- ii. baseline exercise habit: current regular exercise (yes/no), regular aerobic, resistance, and flexibility exercise (yes/no to each), regular home, gym, and outdoor exercise (yes/no to each), exercise intensity;
- iii. Parkinson's disease-related factors: years since diagnosis, leva dopamine equivalent dose, primary Parkinson's disease symptom, patient-reported past year fall count (0, 1-2, 3-12, 13+);
- iv. CYCLE-II characteristics: clinical site, randomized group;
- v. concurrently measured primary and secondary (motor and non-motor) outcomes;
- vi. the same outcome at other visits.

Variables will be imputed by forward order in time with the primary outcome last within each time. At least 25 imputations will be obtained, and trace plots for the primary outcomes will be checked for evident departures for convergence, with burn-in iterations increased until stationarity appears to have been achieved.

Baseline description

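### The imputation model uses no on-study adherence data, so the primary ITT rate difference may be overstated if exercise-arm patients who stop cycling are also more likely to be missing

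*SAP*

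**What the plan says.** SAP, Missing Data, presumes that data are missing at random "conditional on other variables that have been ascertained in CYCLE II". It then narrows the model: "we will multiply impute missing data using both baseline variables and outcome data". The list that follows has six sets: sociodemographics, pre-study exercise habit, Parkinson's-related factors, "CYCLE-II characteristics: clinical site, randomized group", "concurrently measured primary and secondary (motor and non-motor) outcomes", and the same outcome at other visits. The only exercise variables describe habits before the study.

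SAP, Analysis Sets, puts every randomised patient in the inferential analysis, "regardless of their post-randomization experience including treatment and dropout from treatment or study". It also defines a narrower descriptive set of patients whose follow-up was initiated, so it allows for randomised patients who never start.

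On-study exercise is recorded. Protocol, Standardized High-Intensity Home Exercise Program, says the Peloton logs every session and that, whichever ride is chosen, "data are recorded, transmitted and downloaded to the study database regardless". The section on recruitment, screening and randomization gives both arms a Garmin monitor with uploads every 30 days. Specific Aims, Aim 4, uses compliance and other exercise performance variables to predict 12-month MDS-UPDRS III change, and expects time in the heart rate zone and cadence to improve clearly on baseline predictors.

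SAP, Sensitivity analyses, plans complete-case and available-case comparisons. Alternative imputation models are planned only for outcomes with borderline results, and their content is not given.

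**The concern.** A variable that predicts the missing outcome, and may also predict whether it is missing, belongs in a missing-at-random imputation model. By the sponsor's own Aim 4 hypothesis, adherence meets the first condition. It plausibly meets the second, because someone who has given up the programme has less reason to return for an off-medication visit.

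The gap is widest for an exercise-arm patient who stops early and misses both follow-up visits. The concurrent outcomes are missing along with the primary outcome, and the only other visit is baseline. The imputation then rests on baseline and arm, and returns the average course of comparable observed exercise-arm patients. If stoppers are rarer among the observed than among the missing, that average is too favourable.

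The MDS-UPDRS III comparison is at stake. Under the SAP's outcome hierarchy, it gates every claim of benefit. The complete-case and available-case analyses also ignore adherence, so their agreement with the main result would not rule this bias out.

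**Working it through.** The documents give no stopping rate, dropout rate, effect size or SD, so there is no planned figure to reproduce. The size below is illustrative.

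**From the documents:** about 250 patients randomised 1:1, so about 125 per arm; visits at 0, 6 and 12 months; linear time effect. With complete, equally spaced three-visit data and an AR(1) or compound-symmetry covariance, the slope difference equals the difference in mean 12-month change.

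**Assumed:** decline of 3 points/year under usual care or after stopping and 0 while exercising (effect 3); 5% of continuers leave; 10% of usual-care patients leave, unrelated to outcome; slope SD 4; residual SD 5.

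**Closed form.** Let s be the share of the exercise arm that stops and l the share of stoppers who leave.
- Missing share: d = s·l + (1 − s)·0.05
- Stoppers among the observed: p = s(1 − l)/(1 − d)
- Imputed effect: 3(1 − p). True ITT effect: 3(1 − s). Overstatement: 3(s − p)

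| s | l | d | p | Imputed | True | Overstatement |
|---|---|---|---|---|---|---|
| 20% | 30% | 0.100 | 0.14/0.900 = 0.156 | 2.53 | 2.40 | 0.13 (5.6%) |
| 30% | 40% | 0.155 | 0.18/0.845 = 0.213 | 2.36 | 2.10 | 0.26 (12.4%) |
| 40% | 50% | 0.230 | 0.20/0.770 = 0.260 | 2.22 | 1.80 | 0.42 (23.4%) |

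This ignores the 6-month score of patients who leave later. Simulations of the same scenarios that use it (baseline SD 11; 60% of dropouts miss both visits) give slightly smaller values: 0.12 to 0.13, 0.22 to 0.23 and 0.36 to 0.40 points.

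**If stoppers keep half the benefit**, the overstatement becomes 1.5(s − p), which is 0.07, 0.13 and 0.21. Simulation gives half the full-loss values or slightly more.

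**If stopping is unrelated to leaving** (l = 5%), then p = s and the bias is zero. If stoppers leave less often than continuers, the sign reverses.

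**Against sampling error.** The variance of a 12-month change is 4² + 2 × 5² = 66. The SE of the difference with complete data is √(2 × 66/125) = 1.03. The closed-form biases are 0.13/1.03 = 0.13, 0.26/1.03 = 0.25 and 0.42/1.03 = 0.41 SE.

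**Effect of adding adherence.** A perfectly known stopped/continued indicator cuts the bias to 0.012 points or less. A noisy within-arm sessions-per-week covariate, which is closer to what the trial would have, removes about 60% to 77% at almost no cost in precision. That share depends on the assumed noise and falls as the covariate gets noisier.

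**The case against.** A reader might infer that leavers are imputed as if they had kept cycling. The documents do not support that. Strict ITT keeps stoppers who still attend in the observed exercise arm; in the scenarios above they are 16%, 21% and 26% of it, and they inform the imputation. Patients who leave after month 6 also carry their 6-month outcomes into it.

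A reader might also infer that the benefit will be overstated. That needs three conditions the documents do not establish: exercise works, stopping loses the benefit, and stoppers are more common among the missing than among the observed. Specific Aims reports that earlier improvements persisted after exercise ceased, which points to a smaller bias. Outcome-related dropout under usual care could offset it. The largest scenario needs 23% missing in the exercise arm against 10% under usual care, and even then the bias is about 0.4 SE. A bias of that size matters mainly near the significance threshold, where the SAP already provides for alternative imputation models.

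Nor can it be assumed that the data to remove the bias already exist. Medication reconciliation takes place at examinations, so a missed visit yields no levodopa equivalent dose. Garmin data depend on the patient uploading them and on a battery replaced at the 6-month visit. The documents do not say that Peloton transmission continues after withdrawal.

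These points stand, and they limit the size of the concern and the reach of the remedy. They do not close the gap: the Peloton record is unused, and the alternative models are unspecified and triggered only by a borderline result.

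**Conclusion.** The concern holds in a limited form. The primary imputation omits on-study adherence although the trial records it and expects it to predict the primary outcome, and no planned analysis is certain to show the consequence. The primary rate difference may be overstated by about 0.1 to 0.4 points, against an SE near 1.0. That range rests on the assumed 3-point effect, complete loss of benefit on stopping, and assumed stopping and dropout rates.

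The SAP should not be read as contradicting itself. Its missing-at-random sentence is a general statement, and the next sentence openly restricts the model to baseline and outcome data. The point is that the model conditions on less than that general statement allows. Omission of follow-up levodopa equivalent dose is also partly an inference, because the set that lists it is not labelled as baseline. The change is worth making because it is cheap and concerns the gatekeeping outcome.

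**What to change.** In SAP, Missing Data:

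- Impute within randomised arm, or use an arm-specific term, because Peloton data exist only in the exercise arm.
- Add for the exercise arm a simple Peloton summary, such as sessions per week in months 1–6 and 7–12. Count zero only where non-use is confirmed (for example, through the study calls); otherwise treat the value as missing.
- Add Garmin active minutes for the same periods in both arms, where uploaded.
- Treat follow-up levodopa equivalent dose as optional, because it is collected only at attended examinations.
- Make this the primary imputation, and report the current predictor list alongside it as a sensitivity analysis whether or not the result is borderline.

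The cost is SAP wording, linkage of data the trial already collects, and a somewhat larger imputation model, which is why the summaries should be few. The estimate may become slightly less favourable to exercise. Bias removal will be partial, and depends on some stoppers remaining under observation.

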In general, these variables will be described and modeled similarly to secondary outcomes, to potentially support future research. Hypothesis testing results, if obtained, will be interpreted descriptively and not to claim benefit or harm on the basis of CYCLE II data. The distributions of patient-reported falls within the course of the study year across patients within each treatment group will be assessed for compatibility with Poisson distribution. If, as is anticipated, overdispersion is observed, then the negative binomial or other models for overdispersed count data will be entertained.

Adverse events

Adverse events will be descriptively tabulated and compared by Common Terminology Criteria for Adverse Events (CTCAE) system/organ class and preferred term. Serious adverse events will be similarly tabulated and described in individual listings including calendar date and interval from randomization, severity grade (1-5), current status, and assessed relatedness to the exercise intervention. Serious adverse events related to the intervention are expected to be few, and formal hypothesis testing will not be performed due to anticipated low statistical power and the multiple testing context.

Effect modification/subgroup analyses

For those outcomes for which a statistically significant effect of the intervention is found, we will examine statistical interactions of the randomized aerobic exercise regimen with study site, age, sex, BMI, employment status, patient-reported intensity of regular pre-study exercise, primary Parkinson's disease symptoms, primary Parkinson's disease symptom, years since Parkinson's disease diagnosis, whether or not the patient reports any falls during the pre-study year, and baseline MDS-UPDRS III value. For potential categorical effect modifiers, we will focus on an overall Wald test rather than p-values for comparisons of specific subgroups. For continuous variables, we will focus on linear interactions. If a linear interaction is detected, however, we will also assess possible nonlinearity in models using restricted cubic spline effects, and we may also choose to reexpress and communicate the effect in terms of categories defined by ranges to better communicate clinical relevance.

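### The SAP's imputation predictors include no treatment-by-modifier terms, so subgroup interactions tested on the imputed data would be attenuated by up to about the share missing at 12 months

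*SAP*

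**What the plan says.** The SAP's Missing Data section states that "missing data will be multiply imputed by sequential chained equations using fully conditional specification and the following sets of predictors", followed by six sets. The fourth reads "CYCLE-II characteristics: clinical site, randomized group". Most of the variables later used as effect modifiers are in the other sets, each as a predictor in its own right. The last two sets are "concurrently measured primary and secondary (motor and non-motor) outcomes" and "the same outcome at other visits". The list mentions neither products of group with another variable nor imputation within arm; it does not exclude them either.

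On where the imputed values go, the same section says that the inferential analyses "will include the multiply imputed outcome data in analyses". The Analysis Sets section adds: "Inferential and safety outcomes will be analyzed using the inferential and safety analysis set in accordance with the strict intention-to-treat principle". The Treatment effect estimation and testing section fits the models to each imputed data set.

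The Effect modification/subgroup analyses section begins "For those outcomes for which a statistically significant effect of the intervention is found, we will examine statistical interactions". The modifiers are site, age, sex, BMI, employment status, pre-study exercise intensity, primary symptom (listed twice), years since diagnosis, any falls in the prior year, and baseline MDS-UPDRS III: ten distinct variables. No data set is named.

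**The concern.** An imputation model that omits a term which the analysis model then tests is uncongenial with that analysis, and the direction of the error is known. If group enters the equations only as an additive predictor, a patient with no follow-up data is imputed as though the treatment effect were the same in every subgroup. Mixing such values with observed ones dilutes any real interaction.

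Rubin's rules also tend to give too large a variance here, because the imputation model imposes a restriction that the analysis model does not. The estimate shrinks while its standard error stays wide, so power falls.

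The subgroup analyses run only after an outcome has shown a significant treatment effect. That is when readers ask who benefits, and the plan as written would lean toward answering that everyone benefits alike.

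**Working it through.** **Inputs from the documents.** About 250 patients (protocol, Specific Aims); 1:1 allocation (SAP, Overview); visits at 0, 6 and 12 months with time entered linearly; homogeneous AR(1) as default covariance. The documents give no missing share, SD, visit correlation or interaction size, so there is no plan figure to reproduce.

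**Assumptions.** Share missing at 12 months m = 10, 20 or 30%, completely at random and equal by arm unless stated; outcome SD 12; visit correlation AR(1) 0.8, AR(1) 0.9 or compound symmetry (CS) 0.8; a true interaction θ per year that grows linearly in time; other outcomes not used as auxiliary predictors.

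**Step 1: the slope.** With three equally spaced visits and homogeneous AR(1) or CS, the generalized least squares weights for the annual slope are (−1, 0, 1). The slope is therefore Y12 − Y0, and an imputed 6-month value matters only through its part in imputing 12 months.

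**Step 2: share of θ retained.** Let b be the coefficient of Y6 when Y12 is imputed: b = ρ under AR(1), and b = ρ/(1+ρ) under CS.

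- Both follow-up visits missing: the imputed change carries no interaction, so 1 − m is retained.
- Only 12 months missing: the observed 6-month value carries θ/2, and b of that passes to month 12, so 1 − m(1 − b/2) is retained.
- Only 6 months missing: no loss.

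| Pattern | Loss | Loss at m = 20% |
|---|---|---|
| Both visits missing | m | 20% |
| 12 months only, AR(1) 0.8 (b = 0.8) | 0.60m | 12% |
| 12 months only, AR(1) 0.9 (b = 0.9) | 0.55m | 11% |
| 12 months only, CS 0.8 (b = 0.8/1.8 = 0.44) | 0.78m | 16% |
| Half of dropouts have a 6-month value | 0.78m to 0.89m | 16% to 18% |
| 6 months only | 0 | 0 |

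With dropout of 30% in one arm and 10% in the other, both visits missing, the loss is 21% against an average missing share of 20%. Large-sample simulation with both visits missing retained about 0.88–0.93, 0.77–0.83 and 0.65–0.72 at m = 10, 20 and 30%. With the interaction in the imputation model the ratios centred on 1.0. Monte Carlo noise was about 0.05 to 0.10.

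**Step 3: effect at n = 250.** Binary modifier, AR(1) 0.8, θ = 8 points per year, 20 imputations, 250 replicates (Monte Carlo SE of power about 2 to 3 points). Each cell gives additive imputation, then imputation with the interaction.

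| m | Pattern | Mean estimate | Power |
|---|---|---|---|
| 10% | Both missing | 7.0 / 7.8 | 80% / 86% |
| 20% | Both missing | 6.3 / 7.9 | 65% / 80% |
| 20% | 12 months only | 7.0 / 7.9 | 72% / 83% |
| 30% | Both missing | 5.7 / 8.1 | 47% / 76% |
| 30% | 12 months only | 6.4 / 7.8 | 64% / 76% |

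With θ = 0 there was no bias. With both visits missing, the additive version rejected 1.2% of the time at m = 20% and at 30%, against 4.0% and 5.6% with the interaction terms. With only 12 months missing the conservatism was weaker: 4.4% against 4.8% at 20%, and 2.0% against 5.6% at 30%.

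**Step 4: does the remedy survive many terms?** A further simulation used n = 250, SD 12, AR(1) 0.8, θ = 6, m = 20%, all ten modifiers and 15 auxiliary predictors.

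- When 70% of dropouts also missed 6 months, additive imputation gave a mean of 4.85 and 37% power, against 6.13 and 56% with the interaction terms.
- When 30% did, the figures were 5.07 and 44% against 6.06 and 52%.

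The power differences here are 56 − 37 = 19 points and 52 − 44 = 8 points; those at 20% in Step 3 (15 and 11) lie between.

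**The case against.** Two links in the argument rest on silence. The SAP gives sets of predictors, not equations, and never says that group enters additively. The subgroup section does not say that it uses imputed data. Both points stand as limits on certainty. However, the predictor list is introduced as the specification, and the Analysis Sets, Missing Data and Treatment effect sections together leave imputed data as the natural reading. No other data set is offered.

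A reader might infer that every interaction shrinks by the full missing share. The documents do not support that. The same outcome at other visits is a predictor, so an observed 6-month value carries part of the interaction forward. The full share is a ceiling, reached only when both follow-up visits are missing, and observed same-visit outcomes could reduce the loss further. A reader might also suspect the primary result. It is not attenuated by this mechanism, because group is a predictor in the imputation at each visit.

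The consequence is also bounded. The error is conservative and creates no false subgroup claims. The tests are conditional on a significant treatment effect, and the benefit hierarchy gives them no confirmatory role. With about 250 patients, many real interactions would be missed even after correction (52% to 56% power in Step 4). The Sensitivity analyses section already plans complete-case and available-case comparisons, and alternative imputation models for borderline outcomes. These are not tied to the interaction tests, so they mitigate the problem without resolving it.

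**Conclusion.** The concern holds within limits. Followed as written, and with the subgroup tests run on the imputed data, the plan attenuates true treatment-by-modifier interactions by at most about the share missing at 12 months. The loss is about 0.55 to 0.8 of that share where only the 12-month visit is lost, and nil where only the 6-month visit is lost. At an assumed 20% missing, power falls by roughly 8 to 19 percentage points. The actual size cannot be fixed from the documents, because the missing share, SD, visit correlation and interaction size are all assumed. Null interactions and the primary treatment effect are not biased by this mechanism. The point ranks between a minor clarification and something that should be changed, and it is confined to conditional subgroup analyses.

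**What to change.** In the Effect modification/subgroup analyses section, state which data set the interaction tests use. If it is the imputed data, specify a separate imputation for these analyses in one of two ways:

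- Add randomized group × each listed modifier to the equations for follow-up outcomes. Include baseline MDS-UPDRS III, which the current sets do not list as a predictor of follow-up values of the secondary outcomes.
- Impute within each arm (about 125 patients) using a shortened predictor list.

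Report available-case interaction results alongside. Leave the imputation for the primary analysis unchanged: nothing here shows that the richer model would improve it.

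The cost is a few sentences in the SAP and a few lines of code. The downside is a dozen or more extra terms per equation, or fewer auxiliary predictors if imputing by arm, and slightly more variable interaction estimates. Step 4 suggests that the first option still recovers the interaction with all ten modifiers included.

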Usual and Customary Care Group: Participants randomized to the UCC group will be asked to maintain their current exercise habits for 12 months. UCC can entail referrals to physical or occupational therapy or voluntary exercise. Due to the overwhelming evidence that those services are beneficial to individuals with PD, we will not restrict individuals from those programs. Similar to the home exercise group, a member of the study team will call these patients twice per month to inquire about activity levels, medication changes and technology assistance with the activity monitoring device and data.

Alternate Data Capture:

Due to the Covid-19 situation, the Cleveland Clinic and the University of Utah are requesting the ability to conduct virtual visits with participants. The Cleveland Clinic will utilize either FaceTime or Zoom, and the University of Utah will utilize the preferred platforms of their institution.

Inclusion/Exclusion Criteria:

Inclusion Criteria:

- a) Adult with a diagnosis of idiopathic PD by a physician or physician extender
- b) Hoehn and Yahr stage I-III
- c) Demonstrate the ability to safely mount and dismount the Peloton stationary cycle
- d) In-home WiFi (Peloton system requires WiFi to transmit exercise data)*

*2017 report indicates WiFi rates of 76% and 83% in Ohio and Utah households respectively

Exclusion Criteria:

- a) Participation in pharmaceutical or behavioral disease modifying PD-related clinical trial or study
- b) Diagnosis of dementia or any neurocognitive impairment that compromises one's ability to provide informed consent.
- c) Implanted deep brain stimulation electrodes
- d) Recommendation for medical clearance using the American College of Sports Medicine (ACSM) Preparticipation Health Screen (Figure 2)³³
 - a. If the ACSM screen recommends medical clearance, the subject must obtain medical clearance by their health care provider prior to participation.
 - b. Those who choose not to obtain physician clearance will not be eligible for participation. Those who do not receive physician clearance for high intensity exercise will not be eligible.
- e) A musculoskeletal issue (arthritis, osteoporosis, back problem) that would limit one's ability to engage in exercise
- f) Neurological disease other than Parkinson's disease (i.e. multiple sclerosis, Huntington's disease)
- g) Current or active cardiac arrhythmia
- h) DeNovo patients (have not begun Parkinson's disease medications).

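### The imputation model leaves out MDS-UPDRS Parts I, II and IV; self-reported Part II is the measure most likely to be on record when the Part III examination is missing

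*SAP*

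**What the plan says.** The SAP (Missing Data) presumes that unobserved values follow the same distributions as observed ones, "conditional on other variables that have been ascertained in CYCLE II". It then imputes by chained equations from six predictor sets. Sets i to iv hold baseline characteristics, exercise habits, disease factors, site and randomized group. Set v is the "concurrently measured primary and secondary (motor and non-motor) outcomes". Set vi is "the same outcome at other visits".

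The SAP (Study Outcomes) classes MDS-UPDRS Parts I, II and IV as descriptive/exploratory. That puts them outside set v, and no other set names them, even at baseline. The same section says that the last two of these scales, Parts II and IV, focus on "patient-reported experience of functional and social impacts of the effects of motor symptoms". The protocol's outcome table labels only Part II as self-reported, and ticks all three Parts for the same Comprehensive assessment as Part III.

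Under Alternate Data Capture, the protocol says that because of Covid-19 the two sites are "requesting the ability to conduct virtual visits with participants". It does not list the measures to be taken at such visits.

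The SAP (Sensitivity analyses) plans complete-case and available-case comparisons. Alternative imputation models are planned only for outcomes with borderline results, and their predictors are not given.

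**The concern.** The missing-at-random condition is stated for a wider set of variables than the imputation model uses. The gap matters where the unused variable is both informative and observed.

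Part II is the natural candidate. It is the patient's own account of motor impact, so it should correlate with Part III. It also needs neither a medication-free examination nor an instrumented test. The protocol itself concedes that withholding medication is a burden. Suppose a patient declines the Off state or is seen only by video, and Part III and the performance tests are lost. Set v then holds no observed data for that visit, and the best recorded indicator of current motor status goes unused.

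If patients who feel worse are also more likely to miss the Off examination, missingness depends on a recorded variable that the model ignores. The imputed Part III scores in that arm would then be too favourable. If the tendency differs by arm, which is possible because participants know their assignment, the treatment contrast is biased too.

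**Working it through.** **Text check.** Setting the six predictor sets beside the outcome list confirms that Parts I, II and IV are in none of them, while the protocol schedules them at enrollment, 6 and 12 months.

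**Inputs from the documents.** About 250 patients randomized 1:1, so about 125 per arm. The documents give no SD, dropout rate or virtual-visit rate, so there is no planned figure to reproduce.

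**Assumed inputs.**
- m, share of 12-month Part III missing: 0.10-0.30.
- q, share of those patients who still have Part II: 0, 0.5 or 1.
- r, partial correlation of Part II with Part III given the predictors already listed: 0.2-0.6.
- d, how much worse Part II is in those missing Part III than in those observed, in one arm: 0.5 SD.

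**Precision.** In large samples, the variance of an arm mean is proportional to 1/(1-m) without Part II, and to (1-r²)/(1-m) + r²/(1-m(1-q)) with it.

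At m=0.2, r=0.4, q=1: without Part II, 1/0.8 = 1.25; with it, 0.84/0.8 + 0.16 = 1.21. The ratio is 0.968. Effective N rises from 250/1.25 = 200 to 250/1.21 = 207. A simulation of this case gave a ratio of 0.967.

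**Bias.** Without Part II, the bias in the arm's 12-month mean is m·r·d. With it, m(1-q)·r·d remains. The unit is the SD of Part III given the listed predictors.

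| m | r | Variance ratio, q=0 | q=0.5 | q=1 | Bias removed at q=1 (SD) |
|---|---|---|---|---|---|
| 0.1 | 0.2 | 1.000 | 0.998 | 0.996 | 0.01 |
| 0.2 | 0.4 | 1.000 | 0.982 | 0.968 | 0.04 |
| 0.3 | 0.6 | 1.000 | 0.936 | 0.892 | 0.09 |

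At q=0.5 half of the bias is removed; at q=0, none.

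**In points.** If the residual SD is 6-7.5 points (assumed), 0.04 SD is 0.24-0.30 points and 0.09 SD is 0.54-0.68 points.

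**Passage into the primary estimate.** The SAP fits linear time to equally spaced visits. With completed data at 0, 6 and 12 months, the generalised least squares slope weights are (-1, 0, +1) under homogeneous AR(1), the SAP's default, and under compound symmetry. A bias in an arm's 12-month mean therefore enters that arm's annual rate one for one.

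**Against sampling error.** As a rough yardstick, take the contrast of 12-month means with the same m in both arms and bias in one. Its standard error is √(2/(125(1-m))) SD.
- m=0.1, r=0.2: 0.01/0.133 = 0.08 SE.
- m=0.2, r=0.4: 0.04/0.141 = 0.28 SE.
- m=0.3, r=0.6: 0.09/0.151 = 0.60 SE.

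These are upper figures. They take q=1 and no offsetting bias in the other arm.

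**The case against.** The strongest reply is that the required pattern, Part II present and Part III absent, is not documented. All Parts and all performance tests belong to one Comprehensive assessment per time point, so a wholly missed visit or a dropout loses Part II as well. In that case the formula gives no gain. Earlier Part II values entering through set vi would add a little, but not much. This stands, and it is the main reason for the low priority.

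A reader might infer more than the documents support:
- **That the set v outcomes go missing as a block.** This is a reasonable inference from the single-assessment schedule and the Off-state requirement, but neither document says it.
- **That a virtual visit yields Part II but not Part III.** The protocol only asks to be allowed virtual visits. It neither lists their content nor rules out Part III or the cognitive tests.
- **That Part I is patient-reported.** Neither document calls it so.
- **That nothing else informs a missing score.** Part III at other visits remains in the model through set vi, as do the baseline disease factors. Each missing secondary outcome is imputed from its own other visits, so earlier secondary data also reach Part III indirectly.

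It can also be said that no imputation model uses every variable collected, and that choosing auxiliaries from the inferential outcomes is a legitimate judgement. That is fair: this is not a contradiction in the plan.

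The planned sensitivity analyses answer the point only in part. Complete-case and available-case analyses do not use Part II either. Alternative imputation models are tied to borderline results and have no stated predictors, so choosing them then would be data-driven.

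**Conclusion.** The point holds as a cheap improvement, not as an error. The stated missing-at-random condition is wider than the imputation model, and the most useful omitted variable is Part II.

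Under the assumed ranges, adding it lowers the variance of an arm mean by 0-11% and removes up to about 0.09 SD of bias in an arm's 12-month mean. The central case (20% missing, correlation 0.4, Part II always recorded) gives 3% and 0.04 SD. The upper figures need Part II to be recorded for every patient who lacks Part III. There is almost no gain if the two are always missing together. The treatment contrast is biased only if the pattern differs by arm, and nothing in the documents shows that it does.

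A reader might infer that the primary result is materially biased as planned; the documents give no rates that would support this. Priority: optional to low.

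**What to change.** Before unblinded analysis, extend predictor set v of the main imputation model to include MDS-UPDRS Part II, with Parts I and IV as companions. Set vi should then cover their values at other visits. Within each visit, impute them ahead of Part III, in keeping with the SAP's rule that the primary outcome comes last.

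Keep all existing predictors. Nothing in the documents shows that any of them, such as the home, gym and outdoor exercise flags, is dispensable. There is no matching reason to add the Six Minute Walk, a performance test at the same assessment that would probably be lost with the others.

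Report, by arm and visit, how many patients have Part II but not Part III. That count shows whether the change could have mattered.

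The cost is a short SAP edit and about three more incompletely observed variables to impute at each visit, each with its own equation. Convergence checks should cover the enlarged model.
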